8.2 Recording of Adverse Events

At each contact with the subject, the investigator must seek information on adverse events by specific questioning and, as appropriate, by examination. Information on all adverse events should be recorded immediately in the source document, and also in the appropriate adverse event module of the case report form (CRF). All clearly related signs, symptoms, and abnormal diagnostic procedures results should be recorded in the source document, though should be grouped under one diagnosis.

All adverse events occurring during the study period must be recorded. The clinical course of each event should be followed until resolution, stabilization, or until it has been determined that the study treatment or participation is not the cause. Serious adverse events that are still ongoing at the end of the study period must be followed up to determine the final outcome. Any serious adverse event that occurs after the study period and is considered to be possibly related to the study treatment or study participation should be recorded and reported immediately.

8.3 Reporting of Serious Adverse Events and Unanticipated Problems

Investigators and the protocol sponsor must conform to the adverse event reporting timelines, formats and requirements of the various entities to which they are responsible, but at a minimum those events that must be reported within 5 days of PI notification are those that are:

- related to study participation,
- unexpected, and
- Harmful or have the potential to cause harm (see definitions, section 8.1)

Events should be reported using the NYU CTO Medical Events Form (see section 8.3.1 below).

Adverse events that do not fit the above immediately reportable criteria must still be reported to the IRB at each annual review, either in a summary or tabular format.

Incidents or events that meet the OHRP criteria for UPs require the creation and completion of an UP report form. It is the site investigator's responsibility to report UPs to their IRB and to the study sponsor. The UP report will include the following information:

- Protocol identifying information: protocol title and number, PI's name, and the IRB project number;
- A detailed description of the event, incident, experience, or outcome;
- An explanation of the basis for determining that the event, incident, experience, or outcome represents an UP;
- A description of any changes to the protocol or other corrective actions that have been taken or are proposed in response to the UP.

To satisfy the requirement for prompt reporting, UPs will be reported using the following timeline:

- UPs that are SAEs will be reported to the IRB and to the DSMC/study sponsor within 24 hours of the investigator becoming aware of the event.
- Any other UP will be reported to the IRB and to the DSMC/study sponsor within 24 hours of the investigator becoming aware of the problem.

CONFIDENTIAL

- All UPs should be reported to appropriate institutional officials (as required by an institution's written reporting procedures), the supporting agency head (or designee), and OHRP within 5 days of the IR's receipt of the report of the problem from the investigator.

Serious adverse event reporting will begin in conjunction with the date of informed consent. Any SAEs occurring prior to study drug administration that the investigator believes may have been caused by a protocol procedure must be reported immediately to the Sponsor or its designee and recorded on the case report form.

All fatal or life-threatening adverse events must be immediately reported to the Principal Investigator, via appropriate reporting mechanism and the NYU Langone Health IRB by telephone or e-mail. Within 24 hours of the event, the Serious Adverse Event Form must be emailed to [contact] whether full information regarding the event is known or not. Additional follow-up by the investigator will be required if complete information is not known. De-identified source documentation of all examinations, diagnostic procedures, etc. which were completed with respect to the event should be included with the SAE form. Care should be taken to ensure that the patient's identity is protected and the patient's identifiers (as assigned at the time of study enrollment) are properly mentioned on any copy of source document provided to the Sponsor. For laboratory results, include the laboratory normal ranges.

In case of accidental or intentional overdose of study drug (CDX-3379 or trametinib), even if asymptomatic or not fulfilling a seriousness criterion, the overdose is to be reported to the Sponsor immediately (within 1 working day) using the AE and SAE forms supplied by NYU Langone Health PCC. Overdose of study drug will be defined as ≥ 16.5 mg/kg of CDX-3379 and 2 mg of trametinib.

All other serious adverse events must be reported to the sponsor and DSMC within 24 hours by [contact] or e-mail ([contact]). Details are outlined in the study procedure manuals. The Serious Adverse Event Form must also be faxed to the sponsor and DSMC within 24 hours of the event whether full information regarding the event is known or not. Additional follow-up by the investigator will be required if complete information is not known.

Current contact information shall be maintained at the site within the regulatory binder.

All serious adverse events (SAEs) will be evaluated by the DSMC if meeting the requirements for expedited reporting, the Sponsor will report the adverse event to all regulatory authorities with jurisdiction over ongoing trials with the study drug and to all other investigators involved in clinical trials with the study drug. The investigator is responsible for reporting all SAEs to the appropriate IRB, DSMC, and FDA.

For Narrative Reports of Safety Events

If the report is supplied as a narrative, the minimum necessary information to be provided at the time of the initial report includes:

- Study identifier
- Study Center
- Subject number
- A description of the event
- Date of onset
- Current status
- Whether study treatment was discontinued
- The reason why the event is classified as serious
- Investigator assessment of the association between the event and study treatment

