1.6.1.2.1 Management of Toxicity Related to Trametinib

CONFIDENTIAL

This material is the property of the NYU School of Medicine and Langone Medical Center. Do not disclose or use except as authorized in writing by the study sponsor

Table 1. Recommended Dose Modifications for Trametinib

Target Organ	Adverse Reaction^a	Dose Modification
Cutaneous	Grade 2 rash (tolerable)	Continue treatment and monitor
	Intolerable Grade 2 rash or Grade 3 or 4 rash	Withhold Trametinib for up to 3 weeks If improved within 3 weeks, resume Trametinib at a lower dose (reduced by 0.5 mg) or discontinue Trametinib in patients taking Trametinib 1 mg daily
	Intolerable Grade 2 or Grade 3 or 4 rash that does not improve within 3 weeks despite interruption of Trametinib dosing	Permanently discontinue Trametinib
Cardiac	Asymptomatic, absolute decrease in LVEF of 10% or greater from baseline and is below institutional lower limits of normal (LLN) from pretreatment value	Withhold Trametinib for up to 4 weeks. If improved within 4 weeks, resume Trametinib at a lower dose (reduced by 0.5 mg) or discontinue Trametinib in patients taking Trametinib 1 mg daily
	
 - Symptomatic congestive heart failure - Absolute decrease in LVEF of greater than 20% from baseline that is below LLN - Absolute decrease in LVEF of 10% or greater from baseline and is below LLN that does not improve to normal LVEF value within 4 weeks following interruption of Trametinib 	Permanently discontinue Trametinib
Ocular	Grade 2-3 retinal pigment epithelial detachments (RPED)	Withhold Trametinib for up to 3 weeks. If improved to ≤ Grade 1 within 3 weeks, resume Trametinib at a lower dose (reduced by 0.5 mg) or discontinue Trametinib in patients taking Trametinib 1 mg daily. If it does not improve to ≤ Grade 1 within 3 weeks, discontinue Trametinib.

CONFIDENTIAL

Ocular	Retinal Vein Occlusion	Permanently discontinue Trametinib
Pulmonary	Interstitial lung disease/pneumonitis	Permanently discontinue Trametinib
Other	Intolerable Grade 2 adverse reaction Grade 3 adverse reaction	Withhold Trametinib for up to 3 weeks. If Grade 3 adverse reaction improves to \leq Grade 1 following interruption of Trametinib within 3 weeks then reduce dose of Trametinib by 0.5mg or discontinue Trametinib in patients taking Trametinib 1 mg daily.

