5.2 Treatment Regimen

CDX-3379 will be given IV at 15mg/kg every three weeks of a 21-day cycle. Trametinib will be given at a dose of 2 mg PO daily. Treatment will continue until disease progression, intolerable side effects, subject choice, or study closure.

CONFIDENTIAL

This material is the property of the NYU School of Medicine and Langone Medical Center. Do not disclose or use except as authorized in writing by the study sponsor

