5.4.3 Trametinib Storage and Handling

The recommended storage conditions, shelf-life and expiry date, where required, are stated on the product label. Trametinib will be provided as 0.5 mg and 2 mg tablets. Trametinib tablets must be kept refrigerated.

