5.4.4 Trametinib Administration

Trametinib will be administered orally daily at 2 mg (on an empty stomach either one hour prior to or two hours after eating). On days where the subject receives both CDX-7739 and trametinib, the subject will take trametinib immediately following infusion of CDX-3379 (on an empty stomach either one hour prior to or two hours after eating). Do not take a missed dose within 12 hours of the next dose. Subjects are expected to be treated until investigator assessed progressive disease is noted, in the event of unacceptable toxicity, subject choice, or study closure.

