5.5 Subject Compliance Monitoring

CDX-3379 will be administered by study staff, and details regarding each administration will be recorded in the subject's medical record and the CRFs. Trametinib will be self-administered, and a medication diary will be provided to subjects.

CONFIDENTIAL

This material is the property of the NYU School of Medicine and Langone Medical Center. Do not disclose or use except as authorized in writing by the study sponsor

5.6 **Prior and Concomitant Therapy**

No other investigational agents or concurrent therapy for melanoma will be allowed during treatment on this clinical trial.

There are no restrictions on the number of prior therapies, however, subjects may not have been treated previously with an ERBB3 or MEK inhibitor.

Drug Interactions: No formal drug interaction studies have been conducted with trametinib. Trametinib is not a substrate of CYP enzymes or efflux transporters P-gp or BCRP *in vitro*. Based on *in vitro* studies, trametinib is not an inhibitor of CYP450 including CYP1A2, CYP2A6, CYP2B6, CYP2C9, CYP2C19, CYP2D6, and CYP3A4 or of transporters including OATP1B1, OATP1B3, P-gp, and BCRP at a clinically relevant systemic concentration of 0.04 µM. Trametinib is an inhibitor of CYP2C8 *in vitro* (trametinib package insert).

Trametinib is an inducer of CYP3A4 *in vitro*. Based on cross-study comparisons, oral administration of trametinib 2mg once daily with everolimus (sensitive CYP3A4 substrate) 5 mg once daily, had no clinically important effect on the AUC and C_{max} of everolimus (trametinib package insert).

In general, concomitant medications and therapies deemed necessary for the supportive care (e.g., such as anti-emetics, anti-diarrhea) and safety of the subject are allowed.

Subjects are permitted to use the following medications during study treatment:

- Medications to prevent or treat nausea or vomiting.
- Anti-diarrheal medications (e.g., loperamide) for subjects who develop diarrhea.
- Pain medication to allow the subject to be as comfortable as possible.
- Bone targeted therapies (e.g., bisphosphonates, denosumab) to treat bone metastases or to prevent skeletal related events.
- Palliative radiotherapy: any radiotherapy must be listed on the 'Surgical and Medical Procedures' eCRF.
- Immunosuppressive agents to treat suspected AEs.
- Nutritional support or appetite stimulants (e.g., megestrol).
- Oxygen therapy and blood products or transfusions.

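### The trametinib overdose limit in section 8.3 is 2 mg, the assigned daily dose, so as worded it does not separate a correct full dose from a reportable overdose

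*Combined protocol and SAP*

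**What the plan says.** Section 8.3 sets a reporting duty specific to overdose. It begins "In case of accidental or intentional overdose of study drug (CDX-3379 or trametinib), even if asymptomatic or not fulfilling a seriousness criterion" and asks for a report to the sponsor within 1 working day on the AE and SAE forms. The next sentence gives the limits: "Overdose of study drug will be defined as ≥ 16.5 mg/kg of CDX-3379 and 2 mg of trametinib".

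The assigned doses are given elsewhere. For trametinib, section 5.2 says "Trametinib will be given at a dose of 2 mg PO daily" and section 5.4.4 says "Trametinib will be administered orally daily at 2 mg". Section 6.2 starts the drug at the same dose. For CDX-3379, sections 5.2 and 5.4.2 give 15 mg/kg every three weeks. On who takes the tablets, section 5.5 says "Trametinib will be self-administered, and a medication diary will be provided to subjects". No other section gives an overdose limit for trametinib.

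**The concern.** An overdose limit has to lie above the dose the patient is told to take. The CDX-3379 limit lies above the assigned dose; the trametinib limit coincides with it. The purpose of this rule is to bring in overdoses that cause no symptoms and meet no seriousness criterion. Trametinib is taken at home, so an extra tablet is the event for which a site most needs a usable limit. Taken literally, the sentence makes an ordinary correct dose reportable. If sites do not take it literally, each must supply a limit that the protocol does not state.

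**Working it through.** There is no sample size, power or error rate to reproduce. The check compares each limit with the assigned dose, then applies the sentence to a few trametinib doses.

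**Inputs**
- Overdose limits: 16.5 mg/kg for CDX-3379 and 2 mg for trametinib (section 8.3). The only comparison sign stands before the CDX-3379 figure.
- Assigned doses: 15 mg/kg and 2 mg daily (section 5.2).
- Tablets supplied: "Trametinib will be provided as 0.5 mg and 2 mg tablets" (section 5.4.3).

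**Step 1: limit divided by assigned dose**
- CDX-3379: 16.5/15 = 1.10, so the limit is 10% above the assigned dose.
- Trametinib: 2/2 = 1.00, so the limit is the assigned dose.

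**Step 2: classification when CDX-3379 is given correctly at 15 mg/kg**

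The 2.5 mg row is one extra 0.5 mg tablet (2 + 0.5). The 4 mg row is a duplicate 2 mg tablet (2 + 2).

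| Trametinib taken | Sign carried over to trametinib | Sign on CDX-3379 only | Both limits must be met | More than 2 mg (not in the text) |
|---|---|---|---|---|
| 1.5 mg | no | no | no | no |
| 2 mg, the correct full dose | overdose | overdose | no | no |
| 2.5 mg | overdose | no | no | overdose |
| 4 mg | overdose | no | no | overdose |

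**Step 3: which columns the text supports**

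The lead-in sentence names the drugs as alternatives, so each drug has to be judged on its own. That removes the column in which both limits must be met and leaves the first two. In both of these, the correct 2 mg dose counts as an overdose. In the first, it is classed the same as 2.5 mg and 4 mg. In the second, it is classed as an overdose while the larger doses are not. Only the last column gives a sensible result at full dose, and no section of the protocol states it.

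**The case against.** The best answer is that nobody would apply the sentence literally. The duty concerns accidental or intentional overdose, and a prescribed dose taken correctly is neither, so sites would read the limit as more than 2 mg. That is probably what would happen, and a flood of reports on correct doses is not a realistic outcome. It does not rescue the sentence, because the text states no such limit. A sign before the 2 mg could have been lost when the file was converted, but the sentence reads as complete and the sign before the CDX-3379 figure survived.

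The practical harm is also limited. Section 8.1 names drug overdose among the events typically considered serious. Section 8.3.1 has serious events reported within 24 hours, events of clinical interest within 2–5 days, and unapproved deviations affecting safety within 5 working days. These routes depend on a judgement of seriousness or clinical significance, or allow more time, so they soften the gap without closing it. Where the sign is carried over to trametinib, the error is also in the safe direction at full dose: no dose above 2 mg is missed.

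A reader might infer three stronger points, and the documents support none of them.
- **That an overdose of trametinib alone would never be reportable.** This needs the word joining the two limits to mean that both must be met. The lead-in sentence already settles that each drug counts on its own.
- **That a fixed limit is wrong because doses can be reduced.** The dose-modification table in section 1.6.1.2.1 does say "resume Trametinib at a lower dose (reduced by 0.5 mg", and section 3.1 lists trametinib cohorts at 1.5 and 1.0 mg. A patient on 1.0 mg who took one extra 0.5 mg tablet would take 1.5 mg (150% of the prescribed dose) and stay under 2 mg. A fixed limit set against the full protocol dose is nevertheless a legitimate choice, and the same applies to CDX-3379. Section 3.1 lists 10 and 5 mg/kg, so 15 mg/kg given in error would be 15/10 = 150% or 15/5 = 300% of the prescribed dose and still below 16.5 mg/kg. This is a preference to put to the sponsor for both drugs.
- **That the missed-dose rule breaks the definition.** Section 5.4.4 says only "Do not take a missed dose within 12 hours of the next dose". A patient who doses in the evening could take a missed dose the next morning and reach 2 + 2 = 4 mg in one calendar day without error. That matters only if overdose is defined by a daily total, which section 8.3 does not do.

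**Conclusion.** The point holds as a minor error of wording in an operative safety-reporting rule. The trametinib limit is 100% of the assigned dose, and the CDX-3379 limit is 110%. As worded and applied per drug, the trametinib limit does not separate a correct full dose from an overdose reportable within 1 working day. Dosing, dose-limiting toxicities, efficacy and sample size are untouched.

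The conclusion rests on two assumptions: that the published sentence carries no sign before the 2 mg, and that the lead-in sentence governs, so that each drug is judged separately. Confidence is high on the literal point that the limit equals the assigned dose. The documents do not show that any overdose would go unreported in practice.

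**What to change.** Replace the defining sentence in section 8.3 with:

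> Overdose is defined, for either drug separately, as CDX-3379 ≥ 16.5 mg/kg or a trametinib dose of more than 2 mg.

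Optionally, if the sponsor wants excess dosing in dose-reduced patients captured, tie both limits to the currently prescribed dose: for example, at least 110% of the prescribed CDX-3379 dose, or more than the prescribed trametinib dose. For CDX-3379 this gives 1.10 × 15 = 16.5, 1.10 × 10 = 11 and 1.10 × 5 = 5.5 mg/kg. Changing one drug only would leave the same gap in the other. If the sponsor chooses to define the trametinib limit as a total per calendar day, it should add that a permitted late dose counts toward the day it was missed. The replacement sentence above does not need that addition.

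The cost is one sentence in a protocol amendment and a note to sites. Sample size, visits, dosing and analysis do not change.

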8.3.1 Investigator reporting: notifying the study sponsor

Since multiple sites may be participating, the following describes events that must be reported to the study sponsor (NYU Langone Health PCC), Celldex Therapeutics and Novartis in an expedited fashion.

The following describes events that must be reported to the study sponsor in an expedited fashion.

Initial Report: within 24 hours:

CONFIDENTIAL

This material is the property of the NYU School of Medicine and Langone Medical Center. Do not disclose or use except as authorized in writing by the study sponsor

The following events must be reported to the study sponsor (NYULMC PCC) by email within 24 hours of awareness of the event using the NYU CTO Medical Events Form:

- Unanticipated problems related to study participation,
- Serious adverse events, regardless of whether they are unexpected.

The investigator shall maintain a copy of the Medical Events Form on file at the study site. All report forms must be signed and dated by the Principal Investigator. If the Principal Investigator is not available at the time of the initial report, then the form can be submitted by a Sub-Investigator. This form should be reviewed by the Principal Investigator, whom sign/date initial report upon return.

Report to:

[contact]
[contact]

AND

[name], PhD
[name]
[name]
[contact]
[contact]
[contact]

Events of Clinical Interest (any medical event that is deemed significant via Principal Investigator's expertise, but does not apply to SAE categories) will be reported within 2-5 days, or as per study Sponsor specifications.

Follow-up report: within 48 hours:

As a follow-up to the initial report, within the following 48 hours of awareness of the event, the investigator shall provide further information, as applicable, on the unanticipated device event or the unanticipated problem in the form of a written narrative. This should include a copy of the completed Unanticipated Problem form, and any other diagnostic information that will assist the understanding of the event. Significant new information on ongoing unanticipated adverse device effects shall be provided promptly to the study sponsor.

Other Reportable events:

- **Deviations from the study protocol**
Deviations from the protocol must receive both Sponsor and the investigator's IRB approval before they are initiated. Any protocol deviations initiated without Sponsor and the investigator's IRB approval that may affect the scientific soundness of the study, or affect the rights, safety, or welfare of study subjects, must be reported to the Sponsor and to the investigator's IRB as soon as a possible, but **no later than 5 working days** of the protocol deviation.
- **Withdrawal of IRB approval**
An investigator shall report to the sponsor a withdrawal of approval by the investigator's reviewing IRB as soon as a possible, but **no later than 5 working days** of the IRB notification of withdrawal of approval.

Reporting to Celldex

Expedited reporting by investigator to Celldex. *Note that reporting to Celldex is required in addition to reporting to the FDA, as necessary, and does not replace the requirement to notify the FDA, if required.*

CONFIDENTIAL

- NYU will inform Celldex in writing using an SAE form or MEDWATCH 3500A form of any SAE within 24 hours of being aware of the event (see Section 8.1X for the definition of SAE). The written report must be completed and supplied to Celldex by facsimile within 24 hours/1 business day. The initial report must be as complete as possible, including an assessment of the causal relationship between the event and the investigational product(s), if available. Information not available at the time of the initial report (e.g., an end date for the adverse event or laboratory values received after the report) must be documented on a follow-up report.
- Completed SAE reports are to be submitted to:

Celldex Therapeutics, Inc.
Pharmacovigilance
[contact]
Email: [contact] (note-check for removal of HIPAA identifiers prior to sending information)

Reporting to Novartis

To ensure patient safety, every SAE, regardless of suspected causality, occurring after the patient has provided the main informed consent and until at least 30 days after the patient has stopped study treatment must be reported to Novartis within 24 hours of learning of its occurrence.

Any SAEs experienced after this 30 days period should only be reported to Novartis if the investigator suspects a causal relationship to the study treatment. Recurrent episodes, complications, or progression of the initial SAE must be reported as follow-up to the original episode within 24 hours of the investigator receiving the follow-up information. An SAE occurring at a different time interval or otherwise considered completely unrelated to a previously reported one should be reported separately as a new event.

Information about all SAEs is collected and recorded on the Serious Adverse Event Report Form; all applicable sections of the form must be completed in order to provide a clinically thorough report. The investigator must assess and record the relationship of each SAE to each specific study treatment (if there is more than one study treatment), complete the SAE Report Form in English, and send the completed, signed form by fax within 24 hours to the oncology Novartis Drug Safety and Epidemiology (DS&E) department - [contact]). The original copy of the SAE Report Form and the fax confirmation sheet must be kept with the case report form documentation at the study site.

Follow-up information is sent to the same contact(s) to whom the original SAE Report Form was sent, using a new SAE Report Form stating that this is a follow-up to the previously reported SAE and giving the date of the original report. Each re-occurrence, complication, or progression of the original event should be reported as a follow-up to that event regardless of when it occurs. The follow-up information should describe whether the event has resolved or continues, if and how it was treated, whether the blind was broken or not, and whether the patient continued or withdrew from study participation.

If the SAE is not previously documented in the Investigator's Brochure or Package Insert (new occurrence) and is thought to be related to the Novartis study treatment, an oncology Novartis Drug Safety and Epidemiology (DS&E) department associate may urgently require further information from the investigator for Health Authority reporting. Novartis may need to issue an Investigator Notification (IN), to inform all investigators involved in any study with the same drug that this SAE has been reported. Suspected Unexpected Serious Adverse Reactions (SUSARs) will be collected and reported to the competent authorities and relevant ethics committees in accordance with Directive 2001/20/EC or as per national regulatory requirements in participating countries.

Additional safety information collected between IB updates will be communicated in the form of Investigator Notifications. This information will be included in the patient informed consent and should be discussed with the patient during the study as needed.

CONFIDENTIAL

